Appendix 10 Management of Cobimetinib plus Atezolizumab-Associated Adverse Events (Arm A)

Note: For information regarding management of atezolizumab-associated adverse events, please refer to [Appendix 11](#).

Guidelines for Management of Cobimetinib plus Atezolizumab Adverse Events

Event	Action to Be Taken
General guidance for dose modifications and treatment delays and discontinuation	
 • There will be no dose modifications for atezolizumab. • If atezolizumab is withheld and corticosteroids are initiated for an atezolizumab-related toxicity, corticosteroids must be tapered over ≥ 1 month to ≤ 10 mg/day oral prednisone or equivalent before atezolizumab can be resumed.^{a, b, c} 
The dose of cobimetinib can be reduced by 20 mg (one dose level) up to two times (i.e., from 60 mg to 40 mg and then from 40 mg to 20 mg). If further dose reduction is indicated after two dose reductions, the patient must discontinue cobimetinib but may continue treatment with atezolizumab at the investigator's discretion.
 
 • If cobimetinib is withheld for > 28 days because of toxicity, the patient should be discontinued from cobimetinib, unless resumption of treatment is approved by the Medical Monitor after discussion with the investigator. • After dose reduction, consideration may be given to allow for dose escalation of cobimetinib by a maximum of one dose level following resolution of the adverse event that resulted in dose modification, provided there are no safety concerns. • If atezolizumab is withheld for > 12 weeks because of toxicity, the patient should be discontinued from atezolizumab, unless resumption of treatment is approved by the Medical Monitor after discussion with the investigator.
IRRs, CRS, anaphylaxis, and hypersensitivity reaction	
 • Guidelines for management of IRRs and CRS are provided in the Atezolizumab Investigator's Brochure and Appendix 11 • For anaphylaxis precautions, see Appendix 7. • For severe hypersensitivity reactions, permanently discontinue all study treatment.

CRS = *cytokine-release syndrome*; IRR = infusion-related reaction.

^a If corticosteroids have been initiated, they must be tapered over ≥ 1 month to ≤ 10 mg/day oral prednisone or equivalent before atezolizumab can be resumed.

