Appendix 10 Management of Cobimetinib plus Atezolizumab-Associated Adverse Events (Arm A) (cont.)

Table 1 Guidelines for Managing Atezolizumab- and Cobimetinib-Associated Gastrointestinal Toxicity (cont.)

Event	Action to Be Taken
Diarrhea, Grade 2 (intolerable) or Grade 3	
 • Withhold atezolizumab and cobimetinib. • Initiate supportive care and monitor patient closely. • Discontinue medications that may exacerbate colitis (e.g., NSAIDs) while investigating etiology. • Investigate etiology and refer patient to GI specialist for evaluation of possible colitis, including biopsy if appropriate. • If event resolves to Grade 1 or better within 12 weeks, resume atezolizumab at fixed dose. If not, permanently discontinue atezolizumab and cobimetinib. ^{a, b, c} • If event resolves to Grade 1 or better within 28 days, resume cobimetinib with the dose reduced by one level. If not, permanently discontinue cobimetinib.
Diarrhea, Grade 4	
 • Permanently discontinue atezolizumab and cobimetinib, and contact Medical Monitor. ^c • Initiate supportive care and monitor patient closely. • Discontinue medications that may exacerbate colitis (e.g., NSAIDs) while investigating etiology. • Rule out bowel perforation. • Investigate etiology, referring patient to GI specialist for evaluation of possible colitis, including biopsy if appropriate.
Colitis, Grade 1	
 • Continue atezolizumab and cobimetinib. • Initiate supportive care and monitor patient closely. • Discontinue medications that may exacerbate colitis (e.g., NSAIDs). • Refer patient to GI specialist for evaluation and confirmatory biopsy if symptoms persist for > 7 days.
Colitis, Grade 2	
 • Withhold atezolizumab and cobimetinib. • Initiate supportive care and monitor patient closely. • Discontinue medications that may exacerbate colitis (e.g., NSAIDs). • Refer patient to GI specialist for evaluation and confirmatory biopsy. • For recurrent events or events that persist >5 days, initiate treatment with 1–2 mg/kg/day oral prednisone or equivalent. • If event resolves to Grade 1 or better within 12 weeks, resume atezolizumab at fixed dose. If not, permanently discontinue atezolizumab and cobimetinib. ^{a, b, c} • If event resolves to Grade 1 or better within 28 days, resume cobimetinib with the dose reduced by one level. If not, permanently discontinue cobimetinib.

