Appendix 10 Management of Cobimetinib plus Atezolizumab-Associated Adverse Events (Arm A) (cont.)

PULMONARY EVENTS

Pneumonitis is associated with atezolizumab and cobimetinib (see Section Section 5.1.1.1.5 and should be managed according to the guidelines in Table 4.

Table 4 Guidelines for Managing Atezolizumab– and Cobimetinib–Associated Pulmonary Toxicity

Event	Action to Be Taken
Pulmonary events	
General guidance	
 Mild-to-moderate events of pneumonitis have been reported with atezolizumab and cobimetinib. All pulmonary events should be thoroughly evaluated for other commonly reported etiologies such as pneumonia/infection, lymphangitic carcinomatosis, pulmonary embolism, heart failure, chronic obstructive pulmonary disease, or pulmonary hypertension. For events concerning for pneumonitis, consider comprehensive infectious evaluation including viral etiologies.
Pneumonitis, Grade 1 (asymptomatic)	
 Continue atezolizumab and cobimetinib. Re-evaluate on serial imaging. Consider patient referral to pulmonary specialist.
Pneumonitis, Grade 2	
 Withhold atezolizumab and cobimetinib. Refer patient to pulmonary and infectious disease specialists and consider bronchoscopy or BAL. If bronchoscopy is consistent with immune-mediated etiology, initiate treatment with 1–2 mg/kg/day oral prednisone or equivalent. Resume atezolizumab and cobimetinib if event resolves to Grade 1 or better within 12 weeks.^{a, b} Permanently discontinue atezolizumab and cobimetinib and contact Medical Monitor if event does not resolve to Grade 1 or better within 12 weeks.^{a, b, c} For recurrent events, treat as a Grade 3 or 4 event.
Pneumonitis, Grade 3 or 4	
 Permanently discontinue atezolizumab and cobimetinib.^c Refer patient to pulmonary and infectious disease specialists and consider bronchoscopy or BAL. If bronchoscopy is consistent with immune-mediated etiology, initiate treatment with 1–2 mg/kg/day oral prednisone or equivalent. If pulmonary event does not improve within 48 hours or worsens, consider adding an immunosuppressive agent (e.g., infliximab, cyclophosphamide, IVIg, or mycophenolate). If event resolves to Grade 1 or better, taper corticosteroids over ≥ 1 month.

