Appendix 10 Management of Cobimetinib plus Atezolizumab-Associated Adverse Events (Arm A) (cont.)

GUIDELINES FOR MANAGEMENT OF PATIENTS WHO EXPERIENCE HEMORRHAGE

Hemorrhage has been reported with cobimetinib (see Section 5.1.1.1.1) and should be managed according to the guidelines in Table 8.

Table 8 Recommended Dose Modifications in Patients with Hemorrhage

Event	Action to Be Taken
Hemorrhage	
Grade 3 hemorrhage	
 • Interrupt cobimetinib treatment. There are no data on the effectiveness of cobimetinib dose modification for hemorrhage events. Clinical judgment should be applied when considering restarting cobimetinib treatment. • Continue atezolizumab treatment.
Grade 4 hemorrhage or any grade cerebral hemorrhage	
 • Interrupt cobimetinib treatment. Permanently discontinue cobimetinib for hemorrhage events attributed to cobimetinib. • Continue atezolizumab treatment.
Grade 3 or 4 or intolerable Grade 2 treatment-related toxicities not described above and Table 3 (dose modifications for cobimetinib)	
 • Withhold all study treatment. • If event resolves to Grade 1 or better within 12 weeks, resume atezolizumab at fixed dose. If not, permanently discontinue atezolizumab.^{a, b, c} • If event resolves to Grade 1 or better within 28 days, resume cobimetinib with dose reduced by one level. If not, permanently discontinue cobimetinib.

^a If corticosteroids have been initiated, they must be tapered over ≥ 1 month to ≤ 10 mg/day oral prednisone or equivalent before atezolizumab can be resumed.

^b Atezolizumab may be withheld for a period of time beyond 105 days to allow for corticosteroids to be reduced to ≤ 10 mg/day oral prednisone or equivalent. The acceptable length of the extended period of time must be agreed upon by the investigator and the Medical Monitor.

^c Resumption of atezolizumab may be considered in patients who are deriving benefit and have fully recovered from the immune-mediated event. Patients can be rechallenged with atezolizumab only after approval has been documented by both the investigator (or an appropriate delegate) and the Medical Monitor.

Appendix 11

Risks Associated with Atezolizumab and Guidelines for Management of Adverse Events Associated with Atezolizumab

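### For Grade 2 pneumonitis in Arm A, Protocol Appendix 10 gives different default actions for cobimetinib withheld 29 to 84 days and does not say which passage governs

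*Protocol*

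**What the plan says.** The Grade 2 pneumonitis row of Protocol Appendix 10, Table 4 starts with "Withhold atezolizumab and cobimetinib". Two further instructions in that row deal with what follows: "Resume atezolizumab and cobimetinib if event resolves to Grade 1 or better within 12 weeks", and "Permanently discontinue atezolizumab and cobimetinib and contact Medical Monitor if event does not resolve to Grade 1 or better within 12 weeks". Both drugs therefore share one 12-week limit. The table's footnotes on steroid taper, longer withholding and rechallenge speak only of atezolizumab.

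The general guidance that opens Appendix 10 gives the two drugs different limits. For cobimetinib: "If cobimetinib is withheld for > 28 days because of toxicity, the patient should be discontinued from cobimetinib", with the exception "unless resumption of treatment is approved by the Medical Monitor after discussion with the investigator". For atezolizumab: "If atezolizumab is withheld for > 12 weeks because of toxicity, the patient should be discontinued from atezolizumab", with the same exception.

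Several event-specific rows keep the two limits apart. The diarrhea row (intolerable Grade 2, or Grade 3) and the Grade 2 colitis row, for example, give atezolizumab 12 weeks and then set a separate limit for the other drug: "If event resolves to Grade 1 or better within 28 days, resume cobimetinib with the dose reduced by one level. If not, permanently discontinue cobimetinib".

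Protocol Section 5.1.5.1 places general cobimetinib dose modification in its Table 3 and refers to Appendix 10 for specific events. Neither section says that a specific row overrides the general guidance, or the reverse.

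**The concern.** Pneumonitis is listed in Protocol Section 5.1.3 as a potential overlapping toxicity of the two drugs, and in Section 5.2.3 as an event of special interest for immediate reporting. For such an event, sites need one rule on whether and how cobimetinib may restart. A site working from the Table 4 row would restart it in, say, week 8 without asking anyone. A site working from the general guidance would have stopped it after day 28 unless the Medical Monitor had agreed otherwise.

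At stake are patient safety and uniform conduct. Protocol Section 9.4 plans about 160 centers, so like patients could be managed differently, and either course could be logged as a deviation depending on which passage the monitor reads. The exposure summaries and the tables of adverse events leading to discontinuation or interruption (SAP Sections 4.5.1 and 4.5.2) would reflect whichever reading each site took.

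**Working it through.** The plan states the two limits but not the gap between them, so there is no figure of its own to reproduce.

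**Inputs.** Resolution limit in the Table 4 row: 12 weeks. Withholding limit for cobimetinib in the general guidance: more than 28 days. Arm A size: 225 (Protocol Section 3.1.1).

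**Window.** 12 × 7 = 84 days. 84 − 28 = 56 days, that is, days 29 to 84 inclusive. This assumes that both counts start on the same day. The row counts time to resolution and the general rule counts days withheld. If cobimetinib is first withheld k days after onset, and the 12 weeks run from onset, the window is 56 − k days.

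**The two texts side by side, Grade 2 pneumonitis:**

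| Cobimetinib withheld | Table 4 row | General guidance |
|---|---|---|
| Up to day 28, event resolved | Restart | Limit not reached |
| Day 29 to 84, event resolved | Restart; no approval mentioned | Discontinue by default; restart only if the Medical Monitor approves |
| Past day 84, event not resolved | Discontinue permanently | Discontinue by default; same exception |

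Only the middle line conflicts, and only on the default action and the need for approval.

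**Does the row read as a deliberate exception?** Rows that give cobimetinib its own 28-day or 4-week limit are intolerable Grade 2 or Grade 3 diarrhea, Grade 2 and 3 colitis, Grade 3 dermatologic events, Stevens-Johnson syndrome or toxic epidermal necrolysis, Grade 4 or symptomatic CPK elevation, and the catch-all row at the end of Table 8. Rows that withhold cobimetinib without such a limit are AST/ALT above 3 × ULN with bilirubin above 2 × ULN, serous retinopathy, and Grade 3 hemorrhage. That hepatic row, however, requires discussion with the Medical Monitor and gives a restart level. The pattern is mixed, so it does not settle whether the pneumonitis row is intended.

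**How the window is reached.** If bronchoscopy points to an immune cause, the row starts prednisone, and footnote a requires a taper of at least one month before atezolizumab resumes. The row restarts both drugs in one instruction. A site that restarts them together will therefore usually hold cobimetinib past day 28.

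**How many patients.** The only pneumonitis rate near this setting is 1.6%, all grades, with cobimetinib plus vemurafenib (Protocol Section 5.1.1.1.5): 0.016 × 225 = 3.6. No rate is given for the study combination. Assuming 1–5% of any grade: 0.01 × 225 = 2.25 and 0.05 × 225 = 11.25, or about 2 to 11. Under Table 4, Grade 1 continues both drugs and Grade 3 or 4 stops both. Only Grade 2 cases with a restart in the window count, chiefly those resolving on days 29 to 84. The documents give neither the Grade 2 share nor the time to resolution, so 2 to 11 is an upper bound under the assumed rate.

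**The case against.** The strongest reply is that a specific row outranks a general one. Appendix 10 sends pneumonitis to Table 4, Section 5.1.5.1 separates general from event-specific modification, and the final row of Table 8 is reserved for toxicities not covered elsewhere. This reading is natural, but no sentence establishes it, and several other specific rows restate a limit of 28 days or 4 weeks for cobimetinib. It remains possible, not settled.

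Second, a reader might infer that the two passages give opposite instructions. They do not. The general rule has a Medical Monitor exception, and a restart with approval complies with both. This narrows the point to the default action and the approval step, but does not remove it.

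Third, a reader might infer that the pneumonitis row is the only one out of line, or that no restart dose exists anywhere. Neither is supported. Other rows also lack a 28-day limit. The diarrhea, colitis, Grade 3 rash and catch-all rows differ from the general guidance too, because they stop cobimetinib with no approval exception. Table 3 in Section 5.1.5.1 gives general restart doses by grade and occurrence. What is unstated is whether Table 3 applies after Grade 2 pneumonitis.

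Fourth, the practical reach is small. Efficacy is analysed as randomized (SAP Section 4.4), and SAP Section 2.5 says the study will end early. Both statements stand, and they limit the size of the point.

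**Conclusion.** The point holds in a narrow form. For Grade 2 pneumonitis with cobimetinib withheld 29 to 84 days, a 56-day window if both counts start together, the Table 4 row restarts cobimetinib without approval, whereas the general guidance stops it unless the Medical Monitor approves. The protocol does not say which applies.

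The numbers are small and unknown. The figure of 2 to 11 patients is a ceiling that rests on an assumed 1–5% any-grade rate, and should not be read as the number affected. Nor should the 12 weeks be read as a period of resumed dosing; it is the time allowed for the event to resolve. No endpoint, population, sample-size, power or alpha figure changes. The matter is one of safety management and consistent conduct in Arm A, and it is worth correcting because pneumonitis is a listed overlapping toxicity.

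**What to change.** Reconcile the general guidance of Appendix 10 with the Grade 2 pneumonitis row of Table 4. Either state the same limit for resuming cobimetinib in both places, or add a sentence saying which passage governs. In the same edit, state whether the Medical Monitor condition applies to that row and whether the restart doses in Table 3 of Section 5.1.5.1 apply. Which limit or dose is right is for the sponsor's clinical team; no position is taken here.

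The cost is one table row or one sentence in an amendment. With the study ending early, only patients still on Arm A treatment would benefit. No analysis needs to change.

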Appendix 10 Management of Cobimetinib plus Atezolizumab-Associated Adverse Events (Arm A) (cont.)

**Table 4 Guidelines for Managing Atezolizumab– and
Cobimetinib–Associated Pulmonary Toxicity (cont.)**

BAL=bronchoscopic alveolar lavage; IVIg=intravenous immunoglobulin.

- ^a If corticosteroids have been initiated, they must be tapered over ≥ 1 month to ≤ 10 mg/day oral prednisone or equivalent before atezolizumab can be resumed.
- ^b Atezolizumab may be withheld for a period of time beyond 105 days to allow for corticosteroids to be reduced to ≤ 10 mg/day oral prednisone or equivalent. The acceptable length of the extended period of time must be agreed upon by the investigator and the Medical Monitor.
- ^c Resumption of atezolizumab may be considered in patients who are deriving benefit and have fully recovered from the immune-*mediated* event. Patients can be rechallenged with atezolizumab only after approval has been documented by both the investigator (or an appropriate delegate) and the Medical Monitor.

OCULAR EVENTS

Serous retinopathy and retinal vein occlusion is associated with cobimetinib (see Section [5.1.1.1.2](#)) and should be managed according to the guidelines in [Table 5](#).

Appendix 10 Management of Cobimetinib plus Atezolizumab-Associated Adverse Events (Arm A) (cont.)

Table 5 Guidelines for Managing Cobimetinib-Associated Serous Retinopathy and Retinal Vein Occlusion

Description	Management
General guidance	
 • An ophthalmologist should evaluate visual complaints. • Uveitis or episcleritis and other immune-mediated ocular disease may be associated with atezolizumab and may be treated with topical corticosteroid eye drops. Atezolizumab should be permanently discontinued for immune-mediated ocular event that is unresponsive to local immunosuppressive therapy. • Serous retinopathy is associated with cobimetinib. In clinical trials, most events were Grade 1 (asymptomatic) or 2 (symptomatic). Most events in clinical trials resolved or improved to asymptomatic Grade 1 following dose interruption or reduction. If serous retinopathy is diagnosed, cobimetinib should be withheld until visual symptoms improve to Grade 1 or better. Serous retinopathy can be managed with treatment interruption, dose reduction, or with treatment discontinuation. • RVO has been reported in patients treated with MEK inhibitors other than cobimetinib.
Serous retinopathy Severity grade assessment based on NCI CTCAE v4 “Eye Disorders – Other” scale ^{a-d}	
Serous retinopathy, Grade 1^a or 2^b (tolerable):
 
 • Continue cobimetinib and atezolizumab without dose change. • Continue ophthalmology follow-up as clinically indicated. 
Serous retinopathy, Grade 2^b (intolerable) or 3/4^{c/d}:
 
 • Interrupt cobimetinib until Grade \leq 1. • Continue atezolizumab as clinically indicated. • Consult ophthalmology and undergo complete ophthalmologic examination, which includes visual acuity testing, intra-ocular pressure measurements, slit lamp ophthalmoscopy, indirect ophthalmoscopy, visual field, and OCT. Consider a fluorescein angiogram and/or indocyanine green angiogram, if clinically indicated. • Cobimetinib should be dose reduced by 1 dose level when restarting. • Consider permanent discontinuation of cobimetinib if serous retinopathy recurs despite 2 dose level reductions
Retinal vein occlusion Any grade	
 • If RVO (any grade) is diagnosed, cobimetinib dosing should be permanently discontinued and RVO treated per institutional guidelines. • Continue atezolizumab.

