3.3.8 Rationale for Open-Label Design

Study CO39722 is intended to evaluate the efficacy of cobimetinib in combination with atezolizumab in patients with *BRAF*^{V600} wild-type unresectable, locally advanced, or metastatic melanoma compared with pembrolizumab, a widely used standard-of-care treatment in this indication. Study CO39722 is designed as an open-label study for the following reasons:

- Patients receiving cobimetinib are required to undergo safety monitoring tests for MEK inhibitor–associated adverse events, including extensive ophthalmologic tests (requiring a time commitment of approximately 1 hour) and left ventricular ejection fraction (LVEF) monitoring by ECHO or MUGA scan. Both of these investigations will be performed at baseline, after 1 month, and every 3 months thereafter, with additional testing if an abnormality is detected. These assessments are not indicated for patients receiving pembrolizumab monotherapy and would therefore present an excessive and unnecessary burden to patients in the control arm in a blinded study.
- Several adverse events observed with cobimetinib, including serous retinopathy, elevated CPK, and decreased LVEF, are recognized class effects of MEK inhibitors. In the Phase III study GO28141, at the time of the primary analysis, for patients in the cobimetinib plus vemurafenib arm relative to the vemurafenib plus placebo arm, the incidence of these adverse events was as follows: serous retinopathy, 24% versus 2.1%; Grade ≥ 3 elevated CPK, 10.6% versus 0.4%; and Grade ≥ 2 LVEF reductions, 8.5% versus 3.7%. Although the majority of these events have been asymptomatic or mild in nature, they are prospectively monitored in cobimetinib trials and will be monitored in this trial. Because patients in the pembrolizumab control arm will not receive a MEK inhibitor, occurrence of these adverse events would likely alert investigators and patients to the treatment assignment of patients receiving cobimetinib and atezolizumab in the experimental arm, compromising blinding in many cases.

Study CO39722 has been designed to prevent compromise of study outcomes by the absence of blinding. The primary endpoint is independent review committee (IRC)-assessed PFS, and IRC members will be blinded to patient treatment assignment. IRC-assessed PFS will be supported by a secondary endpoint of investigator-assessed

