5.1.1.1.2 Serous Retinopathy

Serous retinopathy (fluid accumulation within the layers of the retina) has been observed in patients treated with MEK-inhibitors, including cobimetinib (Flaherty et al. 2012). Manifestations of serous retinopathy include visual disturbances, findings of retinal detachment, and retinopathy. Serous retinopathy events may also be asymptomatic.

Serous retinopathy has been characterized in Study GO28141. The study incorporated prospective serial ophthalmologic examinations for all enrolled patients. Serous retinopathy was reported more frequently in patients treated with cobimetinib plus vemurafenib than placebo plus vemurafenib (25.5% vs. 2.8%, respectively), and approximately half the events were asymptomatic Grade 1 events. Few patients treated with cobimetinib plus vemurafenib experienced Grade ≥ 3 ocular events (2.8%); the majority of these events were managed with dose modification of both cobimetinib and vemurafenib.

To address serous retinopathy with cobimetinib treatment, all patients are required to undergo a baseline ophthalmologic examination to assess for history or evidence of retinal pathology that is considered to be a risk factor for or indicative of neurosensory retinal detachment, central serous chorioretinopathy, neovascular retinopathy, or retinopathy of prematurity. Patients will also undergo ophthalmologic examinations at specified timepoints throughout the study (see [Appendix 1](#)). Details regarding baseline and subsequent ophthalmologic examinations are provided in Section [4.5.10](#).

Guidelines for management of patients who develop Grade ≥ 2 visual disorders or retinopathy are provided in [Appendix 10](#).

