5.1.5 Management of Patients Who Experience Specific Adverse Events

5.1.5.1 Cobimetinib Dose Modifications

General dose modification for cobimetinib is provided in [Table 3](#). Dose modification for specific adverse events is provided in [Appendix 10](#). After dose reduction, consideration may be given to allow for dose escalation of cobimetinib by a maximum of one dose level (20 mg) increments following resolution of the adverse event that resulted in dose modification, provided there are no safety concerns.

Table 3 Recommended Cobimetinib Dose Modifications

Grade (NCI CTCAE) ^a	Recommended Cobimetinib Dose
Grade 1 or Grade 2 (tolerable)	No dose reduction. Maintain cobimetinib at the same dose of 60 mg QD (3 tablets).
Grade 2 (intolerable) or Grade 3 or 4 (any)	
First appearance	Interrupt treatment until Grade ≤ 1: restart treatment at 40 mg QD (2 tablets).
Second appearance	Interrupt treatment until Grade ≤ 1: restart treatment at 20 mg QD (1 tablet).
Third appearance	Consider permanent discontinuation.

NCI CTCAE=National Cancer Institute Common Terminology Criteria for Adverse Events; QD=once a day.

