Appendix 10 Management of Cobimetinib plus Atezolizumab-Associated Adverse Events (Arm A) (cont.)

Table 5 Guidelines for Managing Cobimetinib-Associated Serous Retinopathy and Retinal Vein Occlusion (cont.)

Description	Management
Potential immune-mediated ocular toxicity (e.g., uveitis, iritis, episcleritis, or retinal events)	
 • For atezolizumab, Follow guidelines provided in the Appendix 11. • Continue cobimetinib as clinically indicated.

ADL = activities of daily living; RVO = retinal vein occlusion.

- ^a Grade 1: Asymptomatic or mild symptoms; clinical or diagnostic observations only; intervention not indicated.
- ^b Grade 2: Moderate; minimal, local or noninvasive intervention indicated; limiting age appropriate instrumental ADL.
- ^c Grade 3: Severe or medically significant but not immediately sight threatening; hospitalization or prolongation of existing hospitalization indicated; disabling; limiting self-care ADL.
- ^d Grade 4: Sight-threatening consequences; urgent intervention indicated; blindness (20/200 or worse) in the affected eye.

GUIDELINES FOR MANAGEMENT OF PATIENTS WHO EXPERIENCE DECREASED LEFT VENTRICULAR EJECTION FRACTION

Decreased left ventricular ejection fraction (LVEF) has been seen with cobimetinib (see Section [5.1.1.1.3](#)) and should be managed according to the guidelines in [Table 6](#).

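### Appendix 10 Table 5 gives two incompatible cobimetinib instructions for a tolerable Grade 2 serous retinopathy, and no text says which governs

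*Protocol*

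**What the plan says.** Protocol Appendix 10, Table 5 covers serous retinopathy in two places.

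- The general guidance row: "If serous retinopathy is diagnosed, cobimetinib should be withheld until visual symptoms improve to Grade 1 or better". It sets no grade or tolerability condition. The sentence after it lists interruption, dose reduction and discontinuation as ways of managing the event; carrying on unchanged is not among them.
- The serous retinopathy row, for Grade 1 or tolerable Grade 2: "Continue cobimetinib and atezolizumab without dose change". For intolerable Grade 2 and for Grade 3/4, the same row interrupts cobimetinib until the event is Grade 1 or lower.

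Footnote b to the table reads "Grade 2: Moderate; minimal, local or noninvasive intervention indicated; limiting age appropriate instrumental ADL". Footnote a describes Grade 1 as without symptoms or with mild ones, needing no intervention.

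Two parts of the main text bear on this. Section 5.1.5.1, Table 3, for Grade 1 or tolerable Grade 2 toxicity in general, says "Maintain cobimetinib at the same dose of 60 mg QD (3 tablets"; the text above that table states "Dose modification for specific adverse events is provided in" Appendix 10. Section 5.1.1.1.2, on serous retinopathy itself, says "Guidelines for management of patients who develop Grade ≥ 2 visual disorders or retinopathy are provided in" Appendix 10.

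**The concern.** The general sentence makes withholding depend on whether symptoms are above Grade 1. The graded row makes it depend, within Grade 2, on whether the event is tolerable. An investigator with a patient who has a moderate but tolerated event finds an instruction to hold and an instruction to continue in the same table.

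The stake is first one of patient management. Serous retinopathy is an adverse event of special interest (Protocol Section 5.2.3), and two sites could handle the same event in opposite ways while each follows the protocol to the letter. The choice then carries into two descriptive safety outputs for Arm A: adverse events leading to interruption of study drug (SAP Section 4.5.2) and dose intensity (SAP Section 4.5.1). Part of what those tables show would reflect which line of Table 5 a site happened to read.

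**Working it through.** No arithmetic applies. The check is to set the two Table 5 instructions side by side for each severity, using the table's own grade definitions, and then to look for a rule of precedence.

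| Severity | General guidance | Graded row | Result |
|---|---|---|---|
| Grade 1 | Threshold for ending a hold is already met | Continue, dose unchanged | No practical conflict |
| Grade 2, tolerable | Hold until Grade 1 or lower | Continue, dose unchanged | **Conflict** |
| Grade 2, intolerable | Hold until Grade 1 or lower | Interrupt until Grade 1 or lower | Consistent |
| Grade 3/4 | Hold until Grade 1 or lower | Interrupt until Grade 1 or lower | Consistent |

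The second line depends on Grade 2 lying above the general threshold. Footnote b settles that: Grade 2 is a moderate event that restricts instrumental activities of daily living, and the definition does not change with tolerability. The general guidance itself labels Grade 2 as symptomatic.

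Search for precedence:

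1. Section 5.1.5.1, Table 3 uses the same tolerable/intolerable split and the same direction as the graded row, but the section refers specific events to Appendix 10.
2. Section 5.1.1.1.2 refers retinopathy of Grade 2 or above to Appendix 10.
3. The ocular events paragraph of Appendix 10 refers the reader to Table 5.
4. Neither Table 5 nor its footnotes say that the row overrides the general guidance, or the reverse.

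Each route ends at the table that contains the conflict.

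Size. The documents give no count or rate of tolerable Grade 2 serous retinopathy. What they do give is:

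- From the Phase III study of cobimetinib plus vemurafenib: "25.5% vs. 2.8%, respectively), and approximately half the events were asymptomatic Grade 1 events" (Section 5.1.1.1.2) and "serous retinopathy, 24% versus 2.1"% (Section 3.3.8). This is a different combination, and the tolerable share of Grade 2 is not reported.
- From the Phase Ib study of cobimetinib plus atezolizumab: lists of events seen in at least 20% of patients, treatment-related in the 22 with melanoma and regardless of attribution in all 150. Serous retinopathy is in neither list. The lists are by term and give no rate below the cut-off.

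These do not combine into an estimate for Arm A.

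**The case against.** The best case for leaving this alone is that the general guidance is a summary and the graded row is the operative rule. The row names the exact event, Table 3 agrees with it, and the general sentence is followed by a loose list of options. Many investigators would probably follow the line that names the grade.

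That reading is reasonable, but no text states it, and general guidance in Appendix 10 is not merely background. The same Table 5 cell contains an instruction on permanently stopping atezolizumab for certain ocular events. The withholding sentence also has the same if-diagnosed form as the plainly operative row on retinal vein occlusion.

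Three further objections stand and limit the point:

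- Reporting within 24 hours applies whether cobimetinib is held or continued, so the special-interest status does not itself create a data problem.
- The interruption and dose-intensity summaries are descriptive and stay valid as records of what happened.
- Tolerable is not defined in Table 5 or its footnotes, so some variation between sites would remain after reconciliation.

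A reader might also infer a second conflict in Appendix 10, between the 12-week window for resuming cobimetinib after Grade 2 pneumonitis and the general rule on holds longer than 28 days. The documents do not show one: the general rule lets the Medical Monitor approve resumption after 28 days.

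**Conclusion.** The point holds as an internal inconsistency confined to tolerable Grade 2 serous retinopathy. It rests on reading both sentences as written and on the absence of any stated precedence.

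A reader might infer that Table 5 contradicts itself on serous retinopathy generally; it does not, since the other severities agree. A reader might apply the 24% to 25.5% from the vemurafenib combination to the 225 patients planned for Arm A and obtain a number affected. The documents do not support that: the drugs differ, the tolerable share is unknown, and the event is absent from the at-least-20% lists for the actual combination. The number affected is not estimable from the documents.

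Nor does the point reach the trial's conclusions. No efficacy analysis, significance level, event count or power figure depends on it. SAP Section 2.5 says the study will be terminated early, which limits the practical reach, although the documents do not say how many patients remain on cobimetinib. It is still worth correcting, because it concerns the handling of a symptomatic eye event and the remedy is small.

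**What to change.** The sponsor's clinical team must reconcile the Table 5 general guidance with the graded row, read with Table 3 in Section 5.1.5.1, so that a single instruction applies to a tolerable Grade 2 serous retinopathy. Which instruction is right is a clinical decision, and no view on it is offered here.

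The cost is a wording change in Appendix 10 and, while any patient is still on cobimetinib, a letter to sites. No new procedure, data collection or analysis is needed.
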